### 10.2. Justification of Sample Size

Based on the initial sample size of 240 patients (prior to this amendment), it is estimated that with 80 patients per group, at the 2-sided 5% significance level, the study will have:

- 97% power to detect a difference of 23% between dupilumab Q2W treatment and placebo treatment (both in combination with TCS) in the percentage of patients who achieve an IGA score 0 or 1 at week 16, assuming that the percentages are 28% and 5% for dupilumab Q2W and placebo, respectively
- 87% power to detect a difference of 17% between dupilumab Q4W treatment and placebo treatment (both in combination with TCS) in the percentage of patients who achieve an IGA score 0 or 1 at week 16, assuming that the percentages are 22% and 5% for dupilumab 300 mg Q4W and placebo, respectively
- 99% power to detect a difference of 51% in the percentages of patients achieving EASI-75 response at week 16, assuming that the percentages are 68% and 17% for dupilumab Q2W and placebo, respectively, (both in combination with TCS)
- 99% power to detect a difference of 45% in percentages of patients achieving EASI-75 response at week 16, assuming that the percentages are 62% and 17% for dupilumab Q4W and placebo, respectively, (both in combination with TCS)

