2.2. Sample Size and Power Considerations

Due to an inadvertent operational error, 68 patients were potentially unblinded. Details about the error and why it may have been unblinding will be described in the clinical study report. An additional approximately 90 patients were added to the study to ensure that the original number of blinded patients for all treatment groups is available for sensitivity analyses that exclude the potentially unblinded patients. This will maintain study balance and power.

Initially it is estimated that with 80 patients per group, at the 2-sided 5% significance level, the study will have a power table shown as below:

	Placebo + TCS (N=80)	Dupilumab 100mg/200mg Q2W + TCS (N=80)			Dupilumab 300mg Q4W + TCS (N=80)		
		Q2W + TCS	Treatment Difference	Power	Q4W + TCS	Treatment Difference	Power
Proportion of patients with IGA score 0 or 1 at week 16 (%)	5%	28%	23%	97%	22%	17%	87%
Proportion of patients with EASI-75 at week 16 (%)	17%	68%	51%	99%	62%	45%	99%

The significance level is set to 2-sided, 0.05 level. At the time the study was designed, there were no data available on the effects of dupilumab in pediatric patients. The assumptions used for the power calculations were estimated based on results from the R668-AD-1224 study (phase 3 combination study with TCS for adult AD patients) and R668-AD-1021 study (a phase 2b dose-ranging study in adults with AD) for patients with IGA=4 at baseline. Based on the result from the R668-AD-1021 study, the efficacy profile for dupilumab 200 mg Q2W was similar to dupilumab 300 mg Q2W. Therefore, the adult efficacy results from dupilumab 300 mg Q2W were used to assume the treatment effect for dupilumab 100mg/200mg Q2W in the study. This was a conservative assumption as it was expected that the effect of dupilumab in children would be greater than that seen in adults. The sample size calculations were done using nQuery (Version 7.0).

[figure not shown]
Adding 90 patients, the total sample size of the study will be up to approximately 330 patients (110 patients per group), or approximately 262 patients (80, 91 and 91 in Q2W, Q4W, and placebo group, respectively) if the potentially unblinded patients are excluded. With the sample size of 330 patients or 262 patients, the power for the co-primary endpoints will be greater than 90%.

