5.7.3. Subgroup Analysis

Subgroup for the primary endpoint and key secondary efficacy will be analyzed based on FAS. The analysis method for the subgroup will be the same as the primary analysis described in Section 5.7.1 and Section 5.7.2. Interactions between the subgroups and treatment groups will also be tested using the logistic regression model for the categorical endpoints, and using the ANCOVA model for the continuous endpoints. The model will include randomization strata, treatment group, subgroup, treatment by randomization strata interaction and treatment by subgroup interaction as factors. P-values for the interaction term will be reported. We will consider interaction effect as significant if P-value is greater than 0.1.

Forest plots of the primary and key secondary efficacy endpoints across subgroups will be generated.

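### At the planned 5% placebo response, ordinary logistic regression gives off-nominal IGA 0/1 subgroup interaction p-values; for weight and region the interaction term is aliased as well

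*SAP*

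**What the plan says.** SAP 5.7.3 analyses subgroups on the FAS for the primary and key secondary endpoints. For binary endpoints the interaction is tested by logistic regression: "The model will include randomization strata, treatment group, subgroup, treatment by randomization strata interaction and treatment by subgroup interaction as factors". The interaction p-value will be reported and judged at 0.1, although the sentence has the direction reversed: "We will consider interaction effect as significant if P-value is greater than 0.1". Below, the intended rule is taken to be p less than 0.1.

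The section does not say whether the test is Wald or likelihood-ratio, whether the strata enter as two factors (weight group and region) or as four cells, or what happens if the model separates or fails to converge. SAP 5.7 lists 24 baseline factors to be considered, among them weight group and region, which are also the stratification factors. SAP 5.7.1 has a Mantel-Fleiss check with a fallback for the primary CMH test; the logistic model has no counterpart.

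The planning rates for IGA 0/1 are in Protocol 10.2: "assuming that the percentages are 28% and 5% for dupilumab Q2W and placebo, respectively", and for the other regimen "assuming that the percentages are 22% and 5% for dupilumab 300 mg Q4W and placebo, respectively". The FAS is planned at about 110 patients per group.

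**The concern.** A maximum-likelihood logistic model needs responders in every placebo subgroup level to give a finite treatment-by-subgroup estimate. With so few placebo responders expected, a level can easily have none. The coefficient then goes to infinity, the Wald standard error grows without limit and the Wald p-value drifts toward 1. The likelihood-ratio statistic remains defined, but its chi-square reference is poor with so few events. The reported p-values are what a reader would use to judge whether the effect on the primary endpoint differs between kinds of patient. Weight is the subgroup of most interest, because the Q2W dose depends on weight group, and it is also one of the two for which the model is redundant.

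**Working it through.** **1. Planning figures.** Protocol 10.2 states "97% power to detect a difference of 23% between dupilumab Q2W treatment and placebo treatment" and "87% power to detect a difference of 17% between dupilumab Q4W treatment and placebo treatment" at 80 per group, two-sided 5%. A pooled two-proportion calculation gives 98.0% and 89.0%; Fisher's exact test gives 97.9% and 87.2%. The stated powers are reproduced to within 2 points, so 5% is the placebo rate on which the plan rests. The documents give no figure for the interaction tests.

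**2. Expected placebo responders.** 0.05 × 110 = 5.5. The smaller placebo count of 91 belongs to the mFAS and does not apply, since subgroups use the FAS.

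**3. Empty placebo levels.** For a two-level subgroup with share s, the probability that a level has no placebo responder is 0.95^(110s) or 0.95^(110(1−s)). At least one is empty with probability 1 − (1 − q1)(1 − q2).

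- 50:50: 0.95^55 = 0.060; 1 − 0.940² = 12%.
- 20% share: 0.95^22 = 0.324 and 0.95^88 = 0.011; 33%.
- 10% share: 0.95^11 = 0.569 and 0.95^99 = 0.006; 57%.

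The shares are assumptions; the documents give none.

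**4. Size of the test, with and without treatment-by-strata.** Simulation under no interaction: 28% v 5%, 110 per arm, one regimen against placebo, 50:50 subgroup, region 60:40, 43% below 30 kg (both splits assumed), 800 runs. The standard error at 10% is √(0.1 × 0.9/800) = 1.1 points.

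| Strata coding | Treatment-by-strata | Any separation | Subgroup coefficient separated | Wald rejects at 0.10 | LR rejects at 0.10 |
|---|---|---|---|---|---|
| Two factors | in | 26% | 11.2% | 3.5% | 12.6% |
| Two factors | out | 11% | 11.2% | 2.9% | 12.8% |
| Four cells | in | 75% | 11.5% | 4.1% | 13.2% |
| Four cells | out | 12% | 11.5% | 3.9% | 13.2% |

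Removing the term clears most of the separation elsewhere in the model, but leaves the subgroup coefficient and its test unchanged within simulation error.

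In the model as written, with region 50:50 or 70:30, a 30% share gives Wald about 5% and LR about 13 to 15%, with the subgroup coefficient separated in 19 to 22% of runs. A 10% share gives Wald about 4% and LR about 8 to 9%, with the coefficient separated in 59 to 62%. The LR excess is therefore a feature of the larger subgroups; the Wald deficit appears at every share.

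**5. Sensitivity to the placebo rate.** At 10% and a 50:50 split, Wald size is about 9% and LR about 11%, close to nominal. The chance of an empty level falls to 1 − (1 − 0.90^55)² = 0.6%; a 20% share level is empty with probability 0.90^22 = 10%, and a 10% share level with probability 0.90^11 = 31%.

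**6. EASI-75.** At 17% v 68% with a 50:50 subgroup, any separation is 0.2% (two factors) or 6% (four cells), and the subgroup coefficient did not separate. Only a very small level is at risk: 0.83^11 = 13% at a 10% share.

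**7. Weight and region.** With strata as two factors and one regimen against placebo, the design has six columns: intercept, weight, region, treatment, treatment × weight, treatment × region. Adding weight as a subgroup supplies weight and treatment × weight again, and the rank stays at 6. With four cells, both added columns are sums of columns already present. The same holds for region.

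**8. Firth penalised likelihood.** With no interaction, its size at nominal 10% was about 6 to 9%. For an assumed dupilumab response of 40% in one level and 10% in the other, placebo 5% and a 20% share, two separate simulations gave power of 28% and 30% (Wald), 33% and 37% (LR), and 39% and 47% (Firth).

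**The case against.** The strongest reply is that little depends on this model. Interaction tests lie outside the testing hierarchy in SAP 5.7.2. Within-subgroup effects use the primary CMH method and are shown in forest plots, so the effect estimates do not come from the logistic fit. The 5% rate is a planning figure from adult studies, and the problem largely fades at 10%. SAP 5.7 lists subgroups to be considered, not a fixed set of tests. All of this stands, and it limits the point to the interpretation of interaction p-values.

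A reader might infer three stronger things that the documents do not support.

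- That the treatment-by-strata term makes the p-values unreliable. Step 4 shows otherwise: an empty placebo stratum sends the strata coefficients to infinity, but the subgroup test is the same with or without that term.
- That separation by stratum is likely. With four equal cells, at least one has no placebo responder with probability 1 − (1 − 0.95^27.5)^4 = 67%, but SAP 5.7.3 does not specify four cells. With weight and region as two factors, an empty level occurs 18 to 39% of the time across the splits examined.
- That real differences will be hidden. This follows only if a Wald test is used. With a likelihood-ratio test and a subgroup share of 30 to 50%, the error is in the other direction.

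**Conclusion.** The point holds in a limited form. With about 5.5 expected placebo responders divided again by each subgroup, the IGA 0/1 interaction p-values from ordinary logistic regression are off-nominal: at 10%, about 5% or less (Wald) or about 12 to 15% (likelihood-ratio) for an evenly split subgroup. The direction depends on a choice that the SAP leaves open. The weakness is essentially one of IGA and rests on the 5% planning rate, on assumed subgroup and strata shares that are independent of each other, and on comparing one regimen with placebo at a time.

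The aliasing for weight and region rests on none of these assumptions. It follows from the model statement, and for those two subgroups the model cannot give the interaction p-value as a separate term.

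Neither part touches the primary analysis or type I error control. This is a minor but worthwhile correction.

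**What to change.** In SAP 5.7.3:

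- Test treatment-by-subgroup for binary endpoints by Firth penalised likelihood, and name the test statistic and the strata coding.
- Omit the treatment-by-strata term, at least for the weight and region subgroups, where this removes the aliasing. For the other subgroups it only reduces separation elsewhere in the model; the p-value is improved by the Firth method.
- While editing the paragraph, correct the direction of the 0.1 threshold.

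The cost is a few lines of SAP text and one software option. The downside is that subgroup models without the term no longer let the treatment effect vary by stratum; the weight and region subgroup analyses already listed show that variation directly. Firth does not create information: power for a small subgroup remains low, as step 8 shows.

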#### 6.2.1. Inclusion Criteria

A patient must meet the following criteria to be eligible for inclusion in the study:

1. Male or female  $\geq 6$  to  $< 12$  years of age at time of screening visit
2. Diagnosis of AD according to the American Academy of Dermatology consensus criteria ([Eichenfield 2003](#)) at screening visit
3. Chronic AD diagnosed at least 1 year prior to the screening visit
4. IGA = 4 at screening and baseline visits
5. EASI  $\geq 21$  at the screening and baseline visits
6. BSA  $\geq 15\%$  at screening and baseline visits
7. Baseline worst itch score weekly average score for maximum itch intensity  $\geq 4$

NOTE: Baseline worst itch average score for maximum itch intensity will be determined based on the average of daily worst itch scores for maximum itch intensity (the daily score ranges from 0 to 10) during the 7 days immediately preceding randomization. A minimum of 4 daily scores out of the 7 days is required to calculate the baseline average score. A complete daily score consists of answers to both questions.

- “What was the worst itch you had today?”
- “What was the worst itch you had last night?”

For patients who do not have at least 4 daily scores reported during the 7 days immediately preceding the planned randomization date, randomization should be postponed until this requirement is met, but without exceeding the 77-day maximum duration for screening plus TCS standardization.

8. With documented recent history (within 6 months before the baseline visit) of inadequate response to topical AD medication(s). For more information, see the note below.

NOTE:

- Inadequate response is defined as failure to achieve and maintain remission or a low disease activity state (comparable to IGA 0=clear to 2=mild) despite treatment with a daily regimen of TCS of medium to high potency ( $\pm$ TCI as appropriate), applied for at least 28 days
  - Patients with documented systemic treatment for AD in the past 6 months are also considered as inadequate responders to topical treatments and are potentially eligible for treatment with dupilumab after appropriate washout.

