3.1. The Efficacy Analysis Sets

The full analysis set (FAS) includes all randomized patients. Efficacy analyses will be based on the treatment allocated at randomization (as randomized). All efficacy variables will be evaluated in the FAS, which will be considered to be the primary analysis set.

The modified full analysis set (mFAS) includes all randomized patients but excludes potentially unblinded patients. The primary endpoint, co-primary endpoint, and selected secondary endpoints will be evaluated in the mFAS as sensitivity analyses.

The per protocol set (PPS) includes all patients in the FAS except for those who are excluded because of major protocol violations. A preliminary list of potential major protocol violations is provided in [Appendix 10.3](#) and a final list will be generated prior to database lock. The PPS will also exclude potentially unblinded patients.

The primary and co-primary endpoints will also be evaluated in the PPS.

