5.7. Analyses of Efficacy Variables

For all efficacy variables, the analysis will be comparisons of each dupilumab regimen and the placebo treatment groups. The following null and alternative hypotheses for the primary endpoint will be tested for each dupilumab regimen group and the placebo group:

H0: $p_{dupilumab} = p_{placebo}$, where p stands for the percent of responders in a treatment group

H1: $p_{dupilumab} \neq p_{placebo}$.

The analyses of efficacy variables are described in the subsections below and summarized in [Appendix 10.1](#).

Subgroups are defined by key baseline factors recorded on the CRF and listed to be considered for primary and key secondary efficacy analyses:

- Age group (≥ 6 to < 9 , ≥ 9 to < 12)
- Sex (Male, Female)
- Ethnicity: Hispanic or Latino (no/yes)
- Race (White, Black or African American, Asian, Other)
- Duration of AD (< 5 years, ≥ 5 years)
- Age of disease onset (< 2 years, ≥ 2 years)

- Age of disease onset (<5 years, ≥5 years)
- Family history of atopic disease (Yes/No)
- Baseline weight group (<30 kg, ≥30 kg)
- BMI (<20, ≥20)
- Region (North America, Europe)
- Baseline severe EASI (<25, ≥25)
- Baseline moderate-to-severe EASI (<20, ≥20)
- Baseline worst itch scale (<7, ≥7)
- Body Surface Area (BSA) (≥10%-<30%, ≥30%-<50%, ≥50%)
- Baseline SCORAD score (<50, ≥50)
- Previous usage of ciclosporin (CsA) (Yes, No)
- Previous usage of methotrexate (MTX) (Yes, No)
- Previous usage of Azathioprine (Aza) (Yes, No)
- Previous use of systemic immunosuppressants for AD (Yes, No)
- History of asthma (Yes, No)
- History of nasal polys (Yes, No)
- History of allergic rhinitis (Yes, No)
- History of food allergies (Yes, No)

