5.7.2. Analyses of Secondary Efficacy Variables

All secondary endpoints will be evaluated on the FAS. Selected secondary endpoints will be evaluated in the mFAS as sensitivity analyses.

The binary secondary efficacy endpoints will be analyzed using the same approaches used for the analysis of the primary endpoints.

The continuous endpoints will be analyzed using analysis of covariance (ANCOVA) model as the primary analysis method with multiple imputation (MI) method for missing data. Patients' efficacy data through week 16 after the rescue treatment use will be set to missing first, and then be imputed by MI method. To account for the uncertainty in the imputation, missing data from the FAS will be imputed 40 times to generate 40 complete data sets by using the SAS procedure MI following the 2 steps below:

Step 1: The monotone missing pattern is induced by Markov Chain Monte Carlo (MCMC) method in MI procedure using seed number 12345. The monotone missing pattern means that if a patient has missing value for a variable at a visit, then the values at all subsequent visits for the same variable are all missing for the patient.

Step 2: The missing data at subsequent visits will be imputed using the regression method for the monotone pattern with seed number 54321 and adjustment for covariates including treatment groups, randomization strata (baseline weight group and region), and relevant baseline.

Once imputations are made, the week 16 data of each of the 40 complete datasets will be analyzed using ANCOVA model with treatment, randomization strata (baseline weight group and region), and relevant baseline included in the model, and the SAS MIANALYZE procedure will be used to generate valid statistical inferences by combining results from the 40 analyses using Rubin's formula.

The imputation model will include:

- The covariates included in the ANCOVA model, including the treatment group, the baseline value and the randomization strata (baseline weight group and region)
- Measured endpoint values at every clinic visit (i.e. week 1, 2, 3, 4, 8, 12 and week 16)

Categorical variables included in above model (i.e., treatment group and randomization strata) are not expected to be missing.

To account for the impact of rescue treatment on the efficacy effect:

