10.3. Potential Major Protocol Violations

*Note: This is a preliminary list and the final list will be generated prior to database lock.

Category	Description of Protocol Deviation
Inclusion Criteria not met but patient randomized	Male or female not ≥ 6 to < 12 years of age at time of screening visit
Inclusion Criteria not met but patient randomized	No diagnosis of AD according to the American Academy of Dermatology consensus criteria (Eichenfield 2003) at screening visit
Inclusion Criteria not met but patient randomized	Chronic AD not diagnosed at least 1 year prior to the screening visit
Inclusion Criteria not met but patient randomized	IGA < 4 at the baseline visit
Inclusion Criteria not met but patient randomized	EASI < 21 at the baseline visit
Inclusion Criteria not met but patient randomized	BSA $< 15\%$ at the baseline visit
Inclusion Criteria not met but patient randomized	Baseline worst itch score weekly average score for maximum itch intensity < 4
Inclusion Criteria not met but patient randomized	Without documented recent history (within 6 months before the baseline visit) of inadequate response to topical AD medication(s)
Inclusion Criteria not met but patient randomized	Has not applied a stable dose of topical emollient (moisturizer) twice daily for at least 11 out of 14 doses during the 7 consecutive days immediately before the baseline visit
Inclusion Criteria not met but patient randomized	Not willing and able to comply with all clinic visits and study-related procedures
Inclusion Criteria not met but patient randomized	Patient, either alone or with help of parents/legal guardians, as appropriate, is not able to understand and complete study-related questionnaires
Inclusion Criteria not met but patient randomized	Parent or legal guardian did not provide signed informed consent. Patients have not provided separate informed assent to enroll in the study, and signed and dated either a separate informed assent form (IAF) or the informed consent form (ICF) was not signed by the parent/legal guardian (as appropriate based on local regulations and requirements).
Exclusion Criteria met but patient randomized	Participation in a prior dupilumab clinical study
Exclusion Criteria met but patient randomized	Treatment with a systemic investigational drug before the baseline visit NOTE: Treatment with a systemic investigational drug refers to treatment received in a clinical study with a drug that is not yet available on the market

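### SAP 5.7.3 inverts the interaction cut-off: P above 0.1 is called significant, so about 90% of null interactions would carry that label

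*SAP*

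**What the plan says.** SAP section 5.7.3 (Subgroup Analysis) applies to the primary and key secondary efficacy endpoints in the FAS. It tests interactions by logistic regression for categorical endpoints and ANCOVA for continuous ones, and specifies the terms: "The model will include randomization strata, treatment group, subgroup, treatment by randomization strata interaction and treatment by subgroup interaction as factors". It then says "P-values for the interaction term will be reported", and gives the decision rule: "We will consider interaction effect as significant if P-value is greater than 0.1". Forest plots across subgroups are also planned.

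The factors are listed in SAP section 5.7, which names 24 to be considered. They include weight group, region and two dichotomies of baseline EASI: one cut at 25, and one labelled "Baseline moderate-to-severe EASI" and cut at 20. Section 5.7.2 defines the strata used in the model as "randomization strata (baseline weight group and region").

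**The concern.** This is the only P-value criterion in either document for judging whether the treatment effect is consistent across subgroups, and it runs backwards. A large interaction P-value is what consistent effects usually produce, and a small one is the signal of heterogeneity. Applied literally, the rule would report consistent effects as significant interactions and would call the clearest heterogeneity not significant.

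The wording cannot be read as a local convention. In its multiplicity text (section 5.7.2) the SAP uses significance in the ordinary sense of a small P-value at the two-sided 0.05 level. The summary table in SAP 10.1 shows which endpoints get subgroup analysis but gives no cut-off.

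Two smaller points affect the same analysis:

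- **Weight group and region.** Both are randomization strata, so the treatment-by-strata interaction already covers them. A separate treatment-by-subgroup term for either essentially repeats what is in the model. The SAP does not say which P-value is then reported.
- **EASI below 20.** Protocol 6.2.1 requires EASI of at least 21 "at the screening and baseline visits". SAP 10.3 lists "EASI < 21 at the baseline visit" as a potential major violation. Because "The full analysis set (FAS) includes all randomized patients", the lower level of this subgroup can hold only patients randomized in violation of entry criteria.

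**Working it through.** The rule is a decision threshold, so the plan has no figure of its own to reproduce. The check is how often the label is attached under the written rule and under its reverse.

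**Step 1: no interaction.** A valid P-value is uniform on (0, 1) under the null.

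- As written: Pr(P > 0.1) = 1 − 0.1 = 0.90.
- Reversed: Pr(P < 0.1) = 0.10.

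**Step 2: simulation of the 5.7.3 model.** Inputs from SAP 2.2:

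- 110 patients per group.
- EASI-75 rates of 17% (placebo), 68% (Q2W) and 62% (Q4W).
- IGA 0/1 rates of 5% (placebo) and 28% (Q2W).

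Assumptions not in the documents:

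- One dupilumab arm against placebo per model.
- Weight, region and subgroup each split 50/50 and independent of one another.
- Strata entered as two factors.
- Likelihood-ratio test for the logistic model.

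There were 4,000 runs per logistic scenario and 8,000 for ANCOVA. The second result column is one minus the first.

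| Scenario | Labelled significant as written (P > 0.1) | With P < 0.1 |
|---|---|---|
| ANCOVA, no interaction | 90.5% | 9.5% |
| EASI-75 Q2W, no interaction (17% v 68% in both levels) | 89.5% | 10.5% |
| EASI-75 Q4W, no interaction (17% v 62% in both levels) | 89.2% | 10.8% |
| IGA 0/1 Q2W, no interaction (5% v 28% in both levels) | 87.4% | 12.6% |
| EASI-75 effect halved in one level (68% and 42.5% v 17%) | 50.1% | 49.9% |
| EASI-75 effect absent in one level (68% and 17% v 17%) | 5.0% | 95.0% |
| IGA effect absent in one level (28% and 5% v 5%) | 43.3% | 56.7% |

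The halved rate is 17% + (68% − 17%)/2 = 42.5%. The IGA null figure is below 90% because placebo responders are sparse.

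A separate three-arm simulation gave null shares of 0.899 (ANCOVA) and 0.877 (logistic, IGA rates). With a true interaction of 0.7 SD in ANCOVA, about 15% of trials gave P > 0.1, so about 85% would be called not significant under the written rule.

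**Step 3: the factor list.** Of the 24 factors, set aside weight, region and the EASI cut at 20: 24 − 3 = 21. If none truly interacts, the expected number labelled significant per endpoint and comparison is:

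- as written, 21 × 0.9 = 18.9;
- reversed, 21 × 0.1 = 2.1.

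The SAP lists the factors only as ones to be considered, so 21 is an upper bound.

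**Step 4: weight and region.** In a two-arm model with two-factor strata, the columns are intercept, treatment, weight, region, treatment-by-weight and treatment-by-region, giving rank 6. Adding weight (or region) as the subgroup, with its treatment interaction, leaves the rank at 6. With a single four-level strata factor the rank is 4 × 2 = 8 and stays at 8. The added interaction therefore has zero degrees of freedom when the CRF and randomization-system values agree. The effect can still be tested through the strata term.

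**The case against.** The strongest reply is that this is plainly a slip, greater written for less. The SAP uses significance in its usual sense elsewhere, every interaction P-value is reported, and forest plots are drawn, so a reader will see heterogeneity whatever label is attached. No estimate, confidence interval, primary conclusion or sample size changes. All of that stands, and it is why the point is limited to the label. It does not justify leaving the rule in place: it is a pre-specified criterion, and reversing it after unblinding would be a departure from the approved plan.

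A second reply is that the heterogeneity figures depend on choices the SAP does not make. That also stands:

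- **Test statistic.** With a Wald test, the IGA shares as written become 96% (no interaction) and 58% (effect absent in one level), instead of 87% and 43%.
- **Subgroup size.** If the level without effect holds only 10% of patients, the absent-effect shares rise from 5% to 45% for EASI-75 and from 43% to 72% for IGA.
- **Number of arms.** A three-arm model raises the halved-effect figure by a few points.

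These results illustrate the rule's behaviour and do not predict this trial. The 90% versus 10% result under no interaction depends only on the P-value being valid, and the direction of the error is the same in every scenario.

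A third reply concerns the side points. SAP 5.7 takes subgroups from the CRF, and SAP 10.3 foresees weight mis-stratification in the randomization system. The treatment-by-weight duplication is therefore exact only when the two sources agree; otherwise the extra term is identified by mis-stratified patients alone. An EASI level below 20 would be nearly empty, and deleting it is housekeeping. Both points are minor.

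**Conclusion.** The concern holds. As written, the rule labels about 90% of null interactions significant instead of about 10%, and the stronger the true heterogeneity, the less often it receives that label. The null figure rests only on a valid P-value. The other percentages rest on the assumed even split, the two-arm model and the likelihood-ratio test. The figure of about 19 null labels instead of about 2 per endpoint and comparison assumes that all 21 factors are tested and none truly interacts.

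The consequence is a wrong statement about subgroup consistency. The interaction tests are outside the hierarchy in SAP 5.7.2, so the primary and key secondary results and their error control are untouched. It should be corrected before database lock.

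**What to change.** In SAP 5.7.3, reverse the inequality so that an interaction is considered significant when its P-value is less than 0.1. This is a one-word change with no effect on data collection, sample size or the primary analysis.

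Optional clarifications in the same revision:

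- For the weight-group and region subgroups, state that the strata enter as two separate factors. Omit the overlapping treatment-by-strata component, and report the P-value from the single treatment-by-weight or treatment-by-region term. The coding has to be fixed first, because a four-level strata factor has no separate component to omit. Say whether the CRF or the randomization-system value is used.
- Delete the EASI subgroup cut at 20; the cut at 25 is already listed.

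Together these cost one clarifying passage and one deleted list item.
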